5.3. Study Population

5.3.1 Selection Criteria

Patient selection criteria for the U-500R Syringe Initiators [Index Event 1a]:

- Include patients who had ≥ 1 prescription claim for U-500R vial during the identification period (VHA and LCED: 01JAN2014-30JUN2017; Truven: 01APR2014-30SEP2017)—the first prescription claim for U-500R vial will be designated as index Event 1a (U-500R syringe initiation), and the date will be designated as the index date;
- Include patients who had ≥ 2 claims with an ICD-9/10-CM code (Appendix 1) for T2DM in any position (primary/secondary) at any time prior to the index date;
- Exclude patients who had both T1DM and T2DM, had no oral anti-diabetic drug (OADs; Appendix 1) other than metformin, and the ratio between the number of T1DM and T2DM claims > 0.5 at any time in the study period (VHA and LCED: 01APR2013-31MAR2018; Truven: 01JUL2013-30JUN2018);
- Include patients who were aged ≥ 18 years on the index date;
- Include patients who had continuous health plan enrollment with medical and pharmacy benefits for ≥ 9 months pre- and post-index event;
- Exclude patients with no evidence of insulin including U-500R (any type; Table 2) in the 9 months pre-index period (baseline);

[2018-7241 Study Identifier] Observational Study Protocol

- Exclude patients with ≥ 1 prescription claim for U-500R use in the 9 months pre-index period;
- Include patients who had ≥ 1 prescription claim for any insulin other than U-500R in the 9-month pre-index period;
- Include patients who had ≥ 1 HbA1c measurement within 90-day pre-index or 30-day post-index event;
- Include patients who had ≥ 1 HbA1c measurement after the 30-day post-index period at any time in the 9-months follow-up period;
 - Patients with ≥ 1 HbA1c measurement after the 30-day post-index and within 30 days prior to the end of the 9-months follow-up period will be flagged; and
 - Patients with ≥ 1 HbA1c measurement after the 30-day post-index and within 2 months prior to the end of the 9-months follow-up period will be flagged;
- Exclude patients who had ≥ 1 claim with a ICD-9/10-CM code (Appendix 1) for secondary diabetes, gestational diabetes, diabetes complicating pregnancy, childbirth, or puerperium, or non-clinical diabetes at any time during the 9-month baseline period;
- Exclude patients who had claims indicating pump use (Appendix 2) in the 9-month post-index (follow-up) period;

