6.4 Other Analyses**6.4.1 Outcomes Analyses**

All the analyses will be performed separately in VHA, linked Truven claims and EMR data, Truven claims database, and the pooled VHA and linked Truven claims and EMR data.

Pooling Multiple Databases

The VHA and linked Truven Claims with EMR databases will be pooled. To remove potential duplicate patient records from multiple data sources, probabilistic matching will be utilized. Potential duplicate patients across the databases will be identified by a STATinMED Research algorithm using age, sex, hospital admission date, hospital discharge date, and primary discharge diagnosis.^{23,24} Identified patients with the same information for the variables listed above will be assumed to be the potential duplicated patient and flagged in the pooled dataset. The rate of duplicate patients is expected to be low based on references and a previous study (<1%).²³ Duplicate patients can be potentially retained in the analytic file if the rate is low. After pooling, we will check if there are any potential duplicates across datasets. If the % will be small (<3%), we will not delete any duplicates because the impact to the final outcomes are considered minimal. If the % is significant (>3%), we will remove the duplicated records from the dataset that has the

[2018-7241 Study Identifier] Observational Study Protocol

larger sample size. Analyses will be conducted on each individual database as well as the pooled dataset.

Research Objective 1: Primary Objective 1Descriptive Analysis

All study variables including demographics, clinical characteristics, and treatment patterns of insulin (i.e., TDD, adherence, prescription fill rate, claim gaps, persistence, and concomitant medication use) will be analyzed descriptively before and after U-500R syringe initiation and U-500R Kwikpen initiation, and before and after U-500R device switch from syringe to Kwikpen.

Numbers and percentages will be provided for dichotomous and polychotomous variables. Means and standard deviations (SDs) will be provided for continuous variables. McNemar's test will be used to determine statistical significance of before and after values for categorical variables, and the paired t-test will be used to assess the statistical significance of before and after values in continuous variables.

Multivariate Analysis

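### The VHA/LCED duplicate check can find only patients whose same hospital stay is in both systems, so a flagged rate below 3% does not show that duplicates are negligible, yet below 3% the plan keeps them

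*Protocol*

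**What the plan says.** Protocol section 6.4.1 (Pooling Multiple Databases) fixes four things itself.

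- **Key.** Duplicates across VHA and LCED are identified "using age, sex, hospital admission date, hospital discharge date, and primary discharge diagnosis".
- **Rule.** "Identified patients with the same information for the variables listed above will be assumed to be the potential duplicated patient", and they are flagged in the pooled file. The same paragraph says that "probabilistic matching will be utilized", although the rule reads as agreement on every field.
- **Expectation.** The duplicate rate is expected to be below 1%, on the strength of cited work.
- **Action.** "If the % will be small (<3%), we will not delete any duplicates because the impact to the final outcomes are considered minimal". Above the limit: "If the % is significant (>3%), we will remove the duplicated records", taken from the larger dataset. No denominator is given for the percentage, and exactly 3% falls under neither branch.

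Entry to the cohorts in section 5.3.1 is by pharmacy claim, for example a "prescription claim for U-500R vial during the identification period" for syringe initiators. Diagnosis, age, enrolment, insulin and HbA1c conditions follow. None of the three cohorts requires an admission. Section 5.1 and Table 1 use the pooled VHA and LCED data for Primary Objectives 1 and 2 and Secondary Objective 2a.

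**The concern.** The check relies on inpatient data in a population selected on outpatient prescriptions. Whatever share of true duplicates it misses, the resulting percentage is compared with 3% as if it measured all of them, and a low value is taken to show that the effect on the outcomes is minimal.

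A person retained twice enters the paired tests and mixed models of the pooled set as two independent patients. The paragraph's stated aim is to remove duplicate records. Below the limit, however, it leaves in place even those already identified, for which removal would cost almost nothing.

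**Working it through.** **1. Which duplicates can match.** Admission date, discharge date and primary discharge diagnosis (3 of 5 fields) need an inpatient stay. A true duplicate falls into one of three groups:

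- no stay: the three fields are empty and only age and sex remain, which cannot identify a person;
- a stay recorded in one system only: the fields disagree;
- the same stay recorded in both: all five fields can agree.

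Only the third group can be found. Section 5.2 describes the VHA inpatient files as covering VHA-provided care, and LCED as MarketScan claims linked to EMR data. Nothing there says that a stay normally appears in both. If empty fields were counted as agreement, patients would match on age and sex alone and be over-flagged. The text does not exclude this.

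**2. The plan's own figure.** The expected rate below 1% comes from cited sources that are not at hand, so it cannot be reproduced.

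**3. What the flagged rate measures.** Let d be the true duplicate rate per pooled patient, h the share of duplicates with a stay, and s the share of those whose same stay is in both systems. Taking all pooled patients as denominator (the natural reading, but not stated) and no false matches:

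flagged rate = d × h × s, and 3% is reached only when d = 3% / (h × s).

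The protocol gives none of d, h or s, so the values below are assumptions.

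| h (s = 100%) | d needed to reach 3% | flagged if d = 1% | flagged if d = 5% | flagged if d = 10% |
|---|---|---|---|---|
| 20% | 15% | 0.2% | 1.0% | 2.0% |
| 30% | 10% | 0.3% | 1.5% | 3.0% |
| 50% | 6% | 0.5% | 2.5% | 5.0% |
| 100% | 3% | 1.0% | 5.0% | 10.0% |

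With s = 50%, every value in the second column doubles.

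**4. Chance of triggering removal.** Take a pool of 4,566: 4,066 VHA Kwikpen patients from Table 4, before the other criteria, plus an assumed 500 from LCED. With d = 5%, the binomial probability that more than 3% are flagged is about 0 at h = 20% or 30%, 0.02 at h = 50%, and about 1 at h = 100%.

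**5. Ceiling on d.** Duplicates cannot exceed the smaller dataset. With 4,066 VHA patients and an assumed 200 LCED patients, d is at most 200 / 4,266 = 4.7%. At h = 30% that would be flagged as 4.7% × 0.30 = 1.4%. With an assumed 500, the ceiling is 500 / 4,566 = 11.0%, flagged as 3.3%.

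**6. Cost of double counting.** If the two copies of a person are perfectly correlated, the variance of a pooled mean is multiplied by 1 + 2d, and its standard error by √(1 + 2d):

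- d = 1%: √1.02 = 1.010
- d = 3%: √1.06 = 1.030
- d = 6%: √1.12 = 1.058

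**7. Effect of changing the denominator.** With d = 5%, h = 30% and s = 100%, 1.5% of all patients are flagged. Divided by patients with a stay, this is 1.5% / 0.30 = 5%, if the pool has the same hospitalised share as the duplicates. With s = 50% it is 0.75% / 0.30 = 2.5%, still too low. The new denominator corrects for h but not for s.

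**The case against.** Several points on the other side stand.

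- **The true rate may be low.** A duplicate must qualify separately in both databases: nine months of enrolment either side of index, a U-500R claim, a baseline insulin claim, and HbA1c values in both windows. If the rate is below 1%, as the protocol expects, the rule says keep even with perfect matching.
- **The effect is modest.** Step 6 gives a standard error about 3% too small at d = 3%.
- **Separate analyses exist.** VHA and LCED are also analysed alone, and the pooled result is not ranked above them.
- **A 3% tolerance is a disclosed choice,** and some flagged matches may be false. The denominator and the handling of blank fields could sit in a SAP.

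None of this rescues the inference from a flagged rate below 3% to minimal impact. The key, the limit, the action and its justification are all fixed in the protocol. Probabilistic weighting would not help either, since age and sex alone cannot identify a patient.

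A reader might infer more than the text supports:

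- **That the check will almost always say keep.** This depends on rates the protocol does not give. At d = 10% and h = 50%, with every shared stay found, 5.0% would be flagged and removed.
- **That the limit is 3% of all patients.** The protocol does not state the denominator.
- **That removing duplicates would repair adherence (PDC), average daily dose or hypoglycemia counts** where care is split between systems. It would not: the retained record stays just as incomplete, and the single-database analyses share that problem.

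**Conclusion.** The point holds in a limited form. As described, the check can identify only duplicates whose same hospital stay is recorded in both systems. Apart from false matches, the flagged percentage is therefore a lower bound on the true rate, and a value below 3% is not evidence that duplicates are negligible. Keeping records already flagged then adds avoidable double counting to the pooled analyses of two primary objectives and one secondary objective.

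The size cannot be established from the protocol. The table in the working rests on assumed values of d, h and s, and the ceiling on an assumed LCED count. The loss of precision is likely to be small if the expected rate below 1% is right. Double counting does not touch the single-database results. The change is worth making because the stated justification is unsound and the correction is cheap, not because a large bias has been shown.

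**What to change.** Amend section 6.4.1 as follows:

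1. Require a non-missing inpatient stay in both records before two patients can be called a match.
2. Remove every flagged duplicate from the larger dataset, whatever the rate. This also settles the unassigned case of exactly 3%.
3. Report the flagged rate with patients who have an inpatient stay as the denominator. Describe it as a lower bound on the duplicate rate in that group, because a stay may appear in only one system. State that duplicates without a stay cannot be detected.
4. Delete the argument that a rate below 3% makes the impact minimal.

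The cost is a few sentences and a changed denominator, with no new data. The downside is that a few flagged records, some of them possibly false matches, leave the pooled set. The change does not address incomplete capture of fills or events for people who use both systems, and should not be presented as doing so.

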- ❖ **Primary Objective 1:** Evaluate the treatment patterns of insulin including observed total daily dose [TDD] in claims, adherence, prescription fill rate, claim gaps, persistence and concomitant medication use among T2DM patients before and after U-500R syringe initiation and U-500R Kwikpen initiation separately as well as before and after U-500R device switch from syringe to Kwikpen:
 - Characterize U-500R Kwikpen patients;
 - Determine differences between treatment patterns before and after U-500R Kwikpen initiation;
 - Determine differences between treatment patterns before and after U-500R syringe initiation; and
 - Determine differences between treatment patterns before and after U-500R device switch from syringe to Kwikpen.

Research Objective 2: Treatment Outcomes

- ❖ **Primary Objective 2:** Evaluate the HbA1c level among T2DM patients before and after U-500R syringe initiation and U-500R Kwikpen initiation separately, as well as before and after U-500R device switch from syringe to Kwikpen:
 - Determine differences between HbA1c level before and after U-500R Kwikpen initiation;
 - Determine differences between HbA1c level before and after U-500R syringe initiation;
 - Determine differences between HbA1c level before and after U-500R device switch from syringe to Kwikpen; and
 - Determine whether observed TDD in claims or insulin adherence played a role in HbA1c changes among U-500R syringe initiators, U-500R Kwikpen initiators, and device switchers from syringe to Kwikpen.
- ❖ **Secondary Objective 2a:** Evaluate the hypoglycemic events among T2DM patients before and after U-500R syringe initiation and U-500R Kwikpen initiation separately, as well as before and after U-500R device switch from syringe to Kwikpen:
 - Determine differences between hypoglycemia events before and after U-500R Kwikpen initiation;
 - Determine differences between hypoglycemia events before and after U-500R syringe initiation;

[2018-7241 Study Identifier] Observational Study Protocol

- Determine differences between hypoglycemia events before and after U-500R device switch from syringe to Kwikpen; and
 - Determine whether observed TDD in claims or insulin adherence played a role in hypoglycemic events among U-500R syringe initiators, U-500R Kwikpen initiators, and device switchers from syringe to Kwikpen.

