- ❖ **Secondary Objective 2b:** Evaluate the treatment outcomes (HbA1c and hypoglycemic events) and prescriber behavior (observed TDD in claims and prescribed TDD from the physician) among T2DM patients before and after U-500R syringe initiation and U-500R Kwikpen initiation separately, as well as before and after U-500R device switch from syringe to Kwikpen in a subset of T2DM patients who had information on HbA1c, prescribed TDD by a physician, and had observed TDD information available in the claim:
- Determine how, in each cohort, the observed TDD in claims differs from the physician-prescribed TDD.
 - Determine, in each cohort, the dynamics between observed TDD in claims, physician-prescribed TDD, and treatment outcomes (HbA1c and hypoglycemic events).

Research Objective 3: Health Care Costs

- ❖ **Primary Objective 3:** Evaluate out-of-pocket costs and total health care costs among T2DM patients before and after U-500R syringe initiation and U-500R Kwikpen initiation separately:
- Evaluate and characterize the dynamic relationship between observed TDD in claims, insulin adherence, and out-of-pocket costs.
 - Evaluate and characterize the dynamic relationship between observed TDD in claims, insulin adherence, and total health care costs.

5. Research Design

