Mixed linear model will be used to evaluate factors associated with HbA1c level in the pre- and post-index periods among U-500R syringe initiators, U-500R Kwikpen initiators, and U-500R device switchers. Mixed linear model is used for studies with a longitudinal feature in which a continuous outcome variable is measured for the same subject repeatedly over the time period. Based on the distribution of the data, observations measured for the same subject are likely to be correlated over the study period and these data are considered as "multilevel" data. In addition, mixed linear model has a mixed effect consisting both fixed and random effects. For this objective, mixed linear model helps to evaluate the effect of both time varying and time-independent variables on the HbA1c, while taking into account for correlation due to multiple assessments from the same individual. In the current model, HbA1c level which is measured at two time intervals (before and after the index event; U-500R initiation/device switch), will be considered the dependent variable. Observed TDD will be considered as the time varying covariate in the model (measured both before and after the index event), and the time independent covariates include the demographic and clinical characteristics.

The complete list of covariates will include:

- age
- sex
- race
- BMI
- baseline CCI score
- observed TDD from claims
- time (pre/post)

Note: Age, sex, race, BMI, and CCI score will be assessed during pre-index period. Observed TDD will be calculated during the entire pre-index and post-index periods, respectively. Pre-index

[2018-7241 Study Identifier] Observational Study Protocol

HbA1c will be defined as the HbA1c measurement -90/+30 days of the index date. For patients with multiple HbA1c measurements within this period, the measurement taken closest to the index event date will be reported as the pre-index HbA1c value. Post-index HbA1c will be defined as the HbA1c within 2 months of the end of the follow-up period.

Adherence will not be included as one of the covariates here due to the high collinearity between time and adherence. Hence, further mediation analysis will be performed to determine the mediator effect of adherence on HbA1c.

Mediation Analysis:

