Zero-inflated negative binomial mixed model will be used to evaluate factors associated with number of hypoglycemia events PPPY in the pre- and post-index periods among U-500R syringe initiators, U-500R Kwikpen initiators, and U-500R device switchers. Zero-inflated negative binomial distribution is a mixture of a binary distribution that is degenerate at zero and an ordinary count distribution such as negative binomial. In cases of outcome variable being repeatedly measured from the individual subjects, zero inflated models are extended to include random effects to account for the correlation among the repeated measures within a subject. In the current model, the number of hypoglycemia events which might have more zeroes (for example not every patient might have a lab visit for glucose) and is measured at two time intervals (before and after the index event; U-500R initiation/device switch), will be considered the dependent variable. Observed TDD, and HbA1c will be considered as the time varying covariates in the model (measured both in the before and after index date), and the time-independent covariates will include the demographic and clinical characteristics.

The complete list of covariates will include:

- age
- sex
- race
- BMI
- baseline CCI score

[2018-7241 Study Identifier] Observational Study Protocol

- observed TDD from claims
- HbA1c
- time (pre/post)

Note: Age, sex, race, BMI, and CCI score will be assessed during pre-index period. Observed TDD and HbA1c will be calculated during the entire pre-index and post-index periods, respectively. Pre-index HbA1c will be defined as the HbA1c measurement -90/+30 days of the index date. For patients with multiple HbA1c measurements within this period, the measurement taken closest to the index event date will be reported as the pre-index HbA1c value. Post-index HbA1c will be defined as the HbA1c within 2 months of the end of the follow-up period.

Research Objective 2: Secondary Objective 2bDescriptive Analysis

Treatment outcomes (HbA1c and number of hypoglycemic events) and prescriber behavior (observed TDD in claims and prescribed TDD from the physician) will be analyzed descriptively and quarterly before and after U-500R syringe initiation and U-500R Kwikpen initiation, and before and after U-500R device switch from syringe to Kwikpen.

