a longitudinal feature in which a continuous outcome variable is measured for the same subject repeatedly over the time period. Based on the distribution of the data, observations measured for the same subject are likely to be correlated over the study period and these data are considered as “multilevel” data. In addition, mixed linear model has a mixed effect consisting both fixed and random effects. For this objective, mixed linear model helps to evaluate the effect of both time varying and time-independent variables on the costs, while taking into account for correlation due to multiple assessments from the same individual. In the current model, costs which are measured at two time intervals (before and after the index event; U-500R initiation), will be considered the dependent variable. Observed TDD will be considered as the time varying covariates in the model (measured both before and after the index date), and the time-independent covariates will include the demographic and clinical characteristics.

The complete list of covariates will include:

- age
- sex
- region
- baseline CCI score
- observed TDD from claims
- Medicare (yes/no)
- time (pre/post)

Note: For all the multivariate analyses the covariates will be included as per the availability in each of the VHA, Truven claims, linked Truven claims and EMR data and pooled VHA and linked Truven data. Age, sex, region, medicare (yes/no), and CCI score will be assessed during pre-index period. Observed TDD will be calculated during the entire pre-index and post-index periods, respectively.

Adherence will not be included as one of the covariates here due to the high collinearity between time and adherence. Hence, further mediation analysis will be performed to determine the mediator effect of adherence on costs.

Mediation Analysis:

Mediation analysis following the Baron and Kenny’s steps will be considered to understand the impact of index event (time) on costs through potential mediators. Adherence is considered as a potential mediator between the costs and time. The key steps in mediation analysis include a model of the mediator (adherence) as a function of the predictor (time) and a model of the outcome (costs) as a function of both the mediator (adherence) and the predictor (time). Bootstrapping method will be used to test the effect of mediator. The detailed steps are described below:

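### The single TDD term in the HbA1c model blends differences between patients with changes within a patient, so it may mislead on whether dose contributed to HbA1c change

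*Protocol*

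**What the plan says.** Section 4.1 of the protocol, under Primary Objective 2, sets the question: "Determine whether observed TDD in claims or insulin adherence played a role in HbA1c changes among U-500R syringe initiators" (and likewise for Kwikpen initiators and device switchers).

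Section 6.4.1 answers it with a mixed linear model that has two HbA1c values per patient, one before and one after the index event. On dose it states: "Observed TDD will be considered as the time varying covariate in the model (measured both before and after the index event". The covariates are introduced with "The complete list of covariates will include", followed by age, sex, race, BMI, baseline comorbidity score, observed TDD and time. The list has no patient-mean TDD, baseline TDD or change in TDD. The mediation analysis that follows concerns adherence only.

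The hypoglycemia model uses the same construction ("Observed TDD, and HbA1c will be considered as the time varying covariates in the model (measured both in the before and after index date"), as does the cost model ("Observed TDD will be considered as the time varying covariates in the model (measured both before and after the index date"). Their objectives are worded differently: "Determine whether observed TDD in claims or insulin adherence played a role in hypoglycemic events" for Secondary Objective 2a, and "Evaluate and characterize the dynamic relationship between observed TDD in claims, insulin adherence, and total health care costs" as one of the two cost questions under Primary Objective 3.

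**The concern.** A question about change in HbA1c is a question within the patient: when this patient's dose moved, did HbA1c move with it? A single raw TDD term in a random-effects model does not estimate that alone. It also draws on the comparison of high-dose with low-dose patients.

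The protocol itself gives reason to expect the two comparisons to differ. Section 3 describes severe insulin resistance as a need for more than 200 units per day and says glucose targets are harder to reach in such patients. High dose is thus a marker of poor control between patients, whereas raising a patient's own dose is meant to lower glucose.

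At stake is the dose part of Primary Objective 2. The sponsor could report no role for dose, or a harmful one, when the within-patient association is favorable. It could also report a role when there is no within-patient association.

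**Working it through.** The protocol gives no effect size, standard deviation or correlation for this model, so there is no figure to reproduce. The inputs below marked as assumed are shown over a range.

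**Inputs**
- From Section 6.4.1: two occasions per patient; TDD entered once; random effects for the patient. The structure is not specified, so a random intercept is assumed.
- From Section 6.3: two-sided 0.05.
- Assumed: r, the pre/post correlation of TDD; ρ, the within-patient correlation of the HbA1c residuals; b_W and b_B, the within- and between-patient slopes in HbA1c points per 100 units, with a TDD standard deviation of 100 units.

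**Formula.** Scale TDD to variance 1 in each period.
- The pre/post difference carries information proportional to (1−r)/(1−ρ) on b_W.
- The pre/post sum carries information proportional to (1+r)/(1+ρ) on b_B.
- The planned coefficient is therefore w·b_W + (1−w)·b_B, where w = (1−r)/[(1−r) + ψ(1+r)] and ψ = (1−ρ)/(1+ρ).

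**Worked case.** For r = 0.7 and ρ = 0.5: ψ = 0.5/1.5 = 0.333, so w = 0.3/(0.3 + 0.333×1.7) = 0.346.

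**Range.** The last column is the planned coefficient when b_W = −0.30 and b_B = +0.30.

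| r | ρ | within weight w | planned coefficient |
|---|---|---|---|
| 0.9 | 0.3 | 0.09 | +0.25 |
| 0.7 | 0.3 | 0.25 | +0.15 |
| 0.7 | 0.5 | 0.35 | +0.09 |
| 0.5 | 0.5 | 0.50 | 0.00 |
| 0.5 | 0.7 | 0.65 | −0.09 |
| 0.3 | 0.7 | 0.75 | −0.15 |
| 0.3 | 0.9 | 0.91 | −0.25 |

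The weight is exactly 0.50 whenever r = ρ. With equal and opposite slopes, the sign is wrong when r exceeds ρ, and right but attenuated when r is below ρ.

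**Simulation check.** One run of 3,000 patients per scenario, with only time and TDD in the model. HbA1c standard deviation 1.4, time effect −0.50 and mean TDD shift +50 units were assumed.
- With b_W = −0.30 and b_B = +0.30, the planned model gave −0.01, +0.09, −0.10 and +0.15 at (r, ρ) = (0.5, 0.5), (0.7, 0.5), (0.5, 0.7) and (0.8, 0.4). The formula gives 0.00, +0.09, −0.09 and +0.18.
- In the same runs, the deviation term of the split model gave −0.36, −0.29, −0.31 and −0.31.
- With b_W = 0 and b_B = +0.20, the planned model gave +0.06 to +0.15, with p<0.001 in all four scenarios.
- With both slopes at −0.20, the planned model gave −0.17 to −0.20, as it should apart from sampling error.

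**Side effect on the time term.** If mean TDD shifts at index, the time coefficient moves by (b_W − planned coefficient) × shift. At r = 0.7 and ρ = 0.5 this is (−0.30 − 0.09) × 0.5 = −0.20, so a true −0.50 is estimated as about −0.70. The simulation also gave −0.70.

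**The case against.** **The size rests on assumed values.** This stands. No r, ρ or slope is in the protocol, and cases with ρ above r keep the right sign. A low r is plausible for initiators, because U-500R replaces or supplements the earlier regimen. That is why the whole range is shown.

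**The planned covariates absorb part of the between-patient confounding.** This also stands. BMI in particular should pick up some insulin resistance, and the simulation contained no such covariates. None of them measures insulin resistance directly, so the adjustment is partial.

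**Coding of a listed covariate can be left to the analysis plan.** In part. A plan not shown here could split the term, and the list names variables, not their coding. But the protocol describes one time-varying TDD covariate in a list it calls complete, and that model as written can mislead.

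**Secondary Objective 2b looks at dose and outcomes quarterly.** It does, but only descriptively and only in the linked claims and EMR data; Section 6.4.1 rules out multivariate analysis for it. It does not isolate the dose-change association.

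**A reader might infer that the dose questions on hypoglycemia and costs will be answered wrongly too.** The documents do not support that. Only Primary Objective 2 asks about changes. The models are presented as searches for associated factors. The hypoglycemia model is zero-inflated negative binomial and the cost model has a log link, so the linear weights do not carry over, and no opposite-sign argument has been made for either outcome.

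**Conclusion.** The point holds for the HbA1c model. Its single TDD coefficient is a blend, with a within-patient share of about 0.09 to 0.91 over r and ρ from 0.3 to 0.9, assuming a random intercept. If the two slopes differ, it may be attenuated, null or of the wrong sign. If they are equal, it is unbiased. The planned model gives no means of telling which case applies.

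It would go too far to say that the model cannot inform the dose question at all, or that its answer will be wrong. Either claim needs slopes that differ, and the protocol makes that plausible without establishing it. In the hypoglycemia and cost models the same mixing arises, but its size and direction are not established. The paired pre/post comparison of HbA1c does not use the TDD term and is unaffected.

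**What to change.** In the HbA1c model, replace the single TDD term with two: the patient's mean TDD over both periods, and each period's deviation from that mean. Test whether the two coefficients differ. Answer the dose part of Primary Objective 2 from the deviation coefficient, and report the patient-mean coefficient as a description of patients. Consider the same split in the hypoglycemia and cost models.

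Report the deviation coefficient as a within-patient association and not as a causal effect. It removes confounding by stable patient characteristics, but dose may be titrated in response to HbA1c. Claims-based TDD is also measured with error: Table 3 derives it from units and days of supply, and Section 5.2 accepts that a fill does not show use.

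**Cost**
- One extra covariate per model, from data already derived.
- A wider interval: in the simulated runs with opposite slopes, the standard error rose from 0.017–0.021 for the single term to 0.019–0.044 for the deviation term.
- More attenuation: with an assumed TDD reliability of 0.8 and true r of 0.7, the within-patient slope keeps 0.8×0.3/(1 − 0.8×0.7) = 0.24/0.44, or about 55% of its size. A null deviation coefficient should therefore be read with caution.
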